9.8. Overdose

On a per dose basis, an overdose is defined as the following amount over the protocol-specified dose of pomalidomide assigned to a given subject, regardless of any associated AEs or sequelae.

- 10% over the protocol-specified dose

On a schedule or frequency basis, an overdose is defined as anything more frequent than the protocol-required schedule or frequency.

Complete data about any overdose, regardless of whether the overdose was accidental or intentional, will be collected on the eCRF page "Investigational Drug Overdose" and will be presented in a listing.

10. PROTOCOL DEVIATIONS/VIOLATIONS

Protocol deviation and protocol violation categories will be defined by the Celgene CSR and/or Clinical Research Physician (CRP). [REDACTED] will identify and manage protocol deviations and protocol violations in a protocol deviation / protocol violation tracker. Additional deviations and violations may be identified by the Celgene CRS and/or CRP during their review of study outputs such as patient profiles and listings. This adjudicated protocol deviation/violation tracker will be maintained by [REDACTED] in an excel file and used for analysis.

Protocol violations will be summarized for the Safety Population using frequency tabulations. Moreover, frequencies will be provided for number of subjects with 1, 2, or > 2 protocol violations.

The summary tables will present data by tumor type/disease indication. A listing of subjects with protocol violations/deviations in the Safety Population will be provided.

11. SAFETY ANALYSIS

The purpose of this section is to define the safety parameters for the study. All summaries of safety data will be conducted using the Safety Population and will be presented by tumor type/disease indication, and in aggregate. Safety measurements will include AEs, clinical laboratory information, vital sign measurements, SPM, pregnancy status, and deaths. Individual subject listings will be provided to support the tables.

11.1. Adverse Events

Adverse Events will be coded according to MedDRA dictionary version 21.0 or higher. The severity of AEs will be graded according to the National Cancer Institute (NCI) Common Terminology Criteria for Adverse Events (CTCAE), version 4.03, May 2009, or later.

All AEs will be recorded by the Investigator from the time the subject signs the ICF/IAF until 28 days after the last dose of pomalidomide and those SAEs made known to the Investigator at any time thereafter that are suspected of being related to pomalidomide.

In the occurrence of partial dates, refer to [Appendix A2 Section 4.1](#) where date the imputation guideline is located.

Treatment-emergent adverse events (TEAEs) are defined as any AE occurring or worsening on or after the first dose of pomalidomide and within 28 days after the last pomalidomide administration date. Adverse events leading to death that occur after 28 days post the last pomalidomide administration but are the end result of an ongoing AE that started during the treatment period, or started prior to first dose of pomalidomide but worsened in severity during the treatment period, are considered treatment-emergent. All TEAEs, AEs leading to IP discontinuation, AEs leading to dose reduction/interruption, AEs related to pomalidomide, and SAEs and AEs leading to death will be summarized by cycle up to a 28-day period after last cycle (refer to [Appendix A2 Section 3](#)), as well as by subject worst recorded grade per event type, SOC, PT and grade. A summary of AEs with NCI CTCAE version 4.03 Grade 3 or higher, as well as the most frequent PTs, will also be provided by grade and PT. If a subject experiences the same AE more than once with different severity grade, then the event with the highest grade will be tabulated in “by grade” tables. If a subject experiences multiple AEs under the same PT/SOC, then the subject will be counted only once for that PT/SOC. In addition, AEs with a missing intensity will be presented in the summary table as an intensity category of “Missing”. Pretreatment AEs will be summarized by PT and SOC.

11.1.1. Overview of TEAEs

The number and percentage of subjects experiencing TEAEs will be summarized in the following categories, although not limited to,:

- All TEAEs;
- TEAEs with severity of grade 3 and/or 4;
- TEAEs with severity of grade 5 (leading to death);
- TEAEs related to pomalidomide;

- TEAEs related to pomalidomide with severity of grade 3 and/or 4;
- Serious TEAEs;
- Serious TEAEs related to pomalidomide;
- TEAEs leading to pomalidomide dose discontinuation;
- TEAEs leading to pomalidomide dose reduction;
- TEAEs leading to pomalidomide dose interruption.

11.1.2. TEAEs by System Organ Class and Preferred Term

The incidence of TEAEs will be summarized by MedDRA SOC and PT. The intensity of AEs will be graded 1 to 5 according to the NCI CTCAE.

Tables summarizing the incidence of TEAEs will be generated for each of the following, although not limited to,:

- All TEAEs;
- TEAEs by severity;
- TEAEs with severity of grade 3 and/or 4;
- TEAEs with severity of grade 5 (leading to death);
- TEAEs related to pomalidomide;
- TEAEs related to pomalidomide by severity;
- TEAEs related to pomalidomide with severity of grade 3 and/or 4;
- Serious TEAEs;
- Serious TEAEs related to pomalidomide;
- TEAEs leading to pomalidomide dose discontinuation;
- TEAEs leading to pomalidomide dose reduction;
- TEAEs leading to pomalidomide dose interruption;
- TEAEs by cycle onset.

System organ classes are sorted by descending order of frequency of SOC, and by descending order of frequency of PT within SOC, according to the overall column.

Treatment emergent adverse events, treatment-related TEAEs, TEAEs of Grade 3 or 4, and treatment-related TEAEs of Grade 3 or 4 will also be analyzed within the following age subgroups:

- Age category (≥ 1 years to < 6 years, ≥ 6 years to < 12 years, and ≥ 12 years).

Listing of AE, SAE, SAE of special interest and AE leading to treatment discontinuation will be provided in separated displays, showing the day in relation to the first dose of pomalidomide that the AE began/ended.

11.2. Adverse Events of Special Interest

Selected TEAEs and serious AEs (SAEs) will form AEs of special interest (AESI), including second malignancies and cardiovascular events, as determined by the mechanism of action, known class effects, or TEAEs observed to date will be summarized. Standardized MedDRA queries (SMQs) will be used in the search strategy for some of the selected AEs of special interest related to study drug, intending to aid in case identification. The groupings of selected AEs, described by one phrase or topic term will be determined by clinicians based on SMQ or relevant search terms and provided to statistician, prior to database lock.

Analysis of AEs of special interest will be presented with tabulations for: summary of TEAEs of interest by category, TEAEs of interest, CTCAE grade 3 or 4 TEAEs of interest, TEAEs of interest related to study medication, CTCAE grade 3 or 4 TEAEs of interest related to study medication, serious TEAEs of interest, serious TEAEs of interest related to study medication, serious CTCAE grade 3 or 4 TEAEs of interest, TEAEs of interest leading to study medication discontinuation, TEAEs of interest by CTCAE maximum grade 1 or 2 and 3 or 4 and TEAEs of interest by CTCAE maximum grade. The following AE of interest categories and preferred terms include, but are not limited to:

- neutropenia;
- febrile neutropenia;
- infection;
- thrombocytopenia;
- hemorrhage and bleeding;
- neuropathy;
- DVT (deep vein thrombosis);
- PE (pulmonary embolism);
- SPM (second primary malignancies);
- muscular weakness;
- glucose intolerance;
- mood alteration;
- cataract;
- cardiovascular events/dysrhythmia;
- fluid retention/edema;
- hematopoietic cytopenias.

The following summaries will be provided for above-mentioned TEAEs of special interest:

- All TEAEs;
- TEAEs with severity of grade 3 and/or 4;

- TEAEs related to pomalidomide;
- Serious TEAEs;
- Serious TEAEs with severity of grade 3 and/or 4;
- Serious TEAEs related to pomalidomide.

All AESIs will be identified by appropriate MedDRA PT.

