9.7. Safety Analysis

Toxicity Assessment

Toxicity, including SPMs, will be monitored in real time during the course of the study. Descriptive statistics will be used to summarize the proportion of subjects experiencing any Grade 3 or higher non-hematologic toxicities and infections.

Adverse Events

Adverse Events will be coded according to the Medical Dictionary for Regulatory Activities (MedDRA) (latest version). This study will utilize the NCI CTCAE (version 4.03) for toxicity grading and performance reporting. All AE data shall be presented by disease stratum and in aggregate, based on the Safety Population, ie, all subjects receiving at least one dose of pomalidomide.

Treatment-emergent adverse events are defined as any AE occurring or worsening on or after the first dose of the study medication until the 28-day post-treatment Safety Follow-up Visit. All TEAEs, AEs leading to study medication discontinuation, AEs leading to dose reduction/interruption, AEs related to the study treatment, SAEs, and AEs leading to death will be summarized by cycle and 28-day follow-up period after permanent treatment discontinuation as well as by subject (worse recorded grade) per event type (organ class and preferred term) and grade. A summary of AEs with NCI CTCAE (version 4.03) Grade 3 or higher, as well as the most frequent preferred terms, will also be provided by grade and term.

Cross tabulations will be provided to summarize frequencies of abnormalities.

By-subject listings will be provided for all relevant safety data. Graphical displays and figures will be provided where useful to assist in the interpretation of results.

Deaths

Deaths during the Treatment Period (defined as the time between enrollment until the 28-day post-treatment Safety Follow-up Visit) and during the Follow-up Period shall be summarized by frequency of occurrence and corresponding percentage by cause of death per study period (during treatment or follow-up) as well as overall. All death data shall be presented by disease stratum and in aggregate.

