10.2.2. Severity/Intensity

For both AEs and SAEs, the Investigator must assess the severity/ intensity of the event.

The severity/intensity of AEs will be graded based upon the subject's symptoms according to the current active minor version of the CTCAE, Version 4.03);

http://ctep.cancer.gov/protocolDevelopment/electronic_applications/ctc.htm#ctc_40

AEs that are not defined in the CTCAE should be evaluated for severity/intensity according to the following scale:

- Grade 1 = Mild – transient or mild discomfort; no limitation in activity; no medical intervention/therapy required
- Grade 2 = Moderate – mild to moderate limitation in activity, some assistance may be needed; no or minimal medical intervention/therapy required
- Grade 3 = Severe – marked limitation in activity, some assistance usually required; medical intervention/therapy required, hospitalization is possible
- Grade 4 = Life-threatening – extreme limitation in activity, significant assistance required; significant medical intervention/therapy required, hospitalization or hospice care probable
- Grade 5 = Death - the event results in death

The term “severe” is often used to describe the intensity of a specific event (as in mild, moderate or severe myocardial infarction); the event itself, however, may be of relatively minor medical significance (such as severe headache). This criterion is *not* the same as “serious” which is based on subject/event *outcome* or *action* criteria associated with events that pose a threat to a subject's life or functioning.

Seriousness, not severity, serves as a guide for defining regulatory obligations.

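### The SAP has no row for the protocol's proportion with Grade 3 or higher non-hematologic toxicity, and its severe infection, age-group and collapsed special-interest rows stop at Grade 4

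*SAP*

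**What the plan says.** Protocol 9.7 makes two requests at the Grade 3 or higher level. One is general: "A summary of AEs with NCI CTCAE (version 4.03) Grade 3 or higher". The other is specific: "the proportion of subjects experiencing any Grade 3 or higher non-hematologic toxicities and infections". Both include fatal events. Protocol 10.2.2 places death at the top of the scale it gives for events that CTCAE does not define ("Grade 5 = Death - the event results in death"), and SAP 11.1.2 confirms the full range: "The intensity of AEs will be graded 1 to 5 according to the NCI CTCAE".

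The SAP treats severity as follows.

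- **SAP 11.1** repeats the general Grade 3 or higher summary, by grade and preferred term. If the same event recurs at different grades, "then the event with the highest grade will be tabulated"; this rule is stated for by-grade tables.
- **SAP 11.1.1** (overview) has a Grade 3 and/or 4 row and a separate Grade 5 row for all TEAEs. For drug-related events the only severe row is "TEAEs related to pomalidomide with severity of grade 3 and/or 4".
- **SAP 11.1.2** has the same rows by system organ class and preferred term, plus by-severity tables for all TEAEs and for related TEAEs. By age it plans all TEAEs, all related TEAEs, and severe tables limited to Grade 3 or 4: "TEAEs of Grade 3 or 4, and treatment-related TEAEs of Grade 3 or 4 will also be analyzed within the following age subgroups".
- **SAP 11.2** lists infection as an AESI category. Its severe AESI rows are all Grade 3 or 4. It plans a collapsed table, "TEAEs of interest by CTCAE maximum grade 1 or 2 and 3 or 4", followed by a table of each maximum grade without grouping.
- **SAP 11.3** tabulates deaths by primary cause, by tumor type and in aggregate, not by age.

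**The concern.** Safety is a secondary objective, described in both documents as the type and rate of treatment-related toxicity. A severe-event rate that stops at Grade 4 can leave out the worst outcome. This matters most for infection. Protocol 1.2.3 names infections as the most frequent serious events in the adult studies. Protocol 1.2.4 reports myelosuppression as the main toxicity in the pediatric Phase 1 study, where a Grade 3 lung infection was among the dose-limiting toxicities. Age matters too, because protocol 6.4.2 says experience below 3 years is limited and asks for careful monitoring.

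Two things are at stake. A proportion that the protocol specifies would not be produced if the SAP were followed as written. And some severe rates, in particular those by age, could look lower than the corresponding Grade 3 or higher rates without the reader being able to tell.

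**Working it through.** Neither document states a figure to reproduce here. The check compares grade bands, followed by a scale calculation.

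**Step 1. What each cut provides**

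| Cut | Severe row covers | Where Grade 5 can be seen | Combined Grade 3 or higher row |
|---|---|---|---|
| All TEAEs | 3 and/or 4 | Own row (11.1.1, 11.1.2); by-severity table | Yes, by grade and preferred term (11.1) |
| Related TEAEs | 3 and/or 4 | By-severity table (11.1.2); worst-grade summary (11.1) | None |
| AESIs, including infection | 3 or 4 | Ungrouped maximum-grade table (11.2) | None |
| Age groups | 3 or 4 | Only inside all-TEAE and all-related totals | None |
| Non-hematologic toxicity | No row | Not applicable | None, though protocol 9.7 asks for it |

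**Step 2. Can the protocol 9.7 proportion be recovered from other tables?** For non-hematologic toxicity, no. The general summary is by preferred term, and one child can contribute to several terms, so adding rows counts events more than once and does not give a number of subjects. For infection it can be recovered if the ungrouped maximum-grade table is shown at category level: the Grade 3, 4 and 5 counts then add up. No planned row states the result.

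**Step 3. The collapsed AESI table.** Grades run 1 to 5 and the bands are 1-2 and 3-4. A subject with a maximum of 5 fits neither band. As soon as one fatal AESI occurs, the two bands no longer add up to all subjects with that AESI. Here the loss is certain.

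**Step 4. The other Grade 3 and/or 4 rows.** The SAP does not say whether these rows count a subject with any event at Grade 3 or 4, or only a subject whose maximum is 3 or 4. On the natural reading (any event), a child with a fatal event and a separate Grade 3 or 4 event in the same cut is still counted. Only a child whose sole Grade 3 or higher event in that cut is fatal is missed. On that reading a child can also appear in both the Grade 3 and/or 4 row and the Grade 5 row, so adding the two need not give the Grade 3 or higher rate.

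**Step 5. Scale.** Let f be the number of subjects missed and n the denominator. The shortfall is f/n. With f = 1:

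- n = 9 (Stage 1 of one stratum): 1/9 = 11.1 points
- n = 20 (full stratum): 1/20 = 5.0 points
- n = 80 (all strata, full enrollment): 1/80 = 1.25 points

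Illustration with assumed counts:

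- 6 of 20 subjects at Grade 3 or higher is 30.0%. A Grade 3 or 4 row shows 5/20 = 25.0% if one of them is fatal-only, and 4/20 = 20.0% if two are.
- 3 of 9 is 33.3%. The row shows 2/9 = 22.2% or 1/9 = 11.1%.

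The sizes 9, 20 and 80 are the planned evaluable numbers (protocol 9.3). Safety tables use everyone dosed, including subjects later replaced, so actual denominators may be somewhat larger and the shortfall smaller. Age-group sizes are not given, so the same formula applies there with n unknown.

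**The case against.** The strongest reply is that deaths are not hidden and that this is a matter of layout. Much of that stands. A reader might infer that fatal cases vanish from the severe rates throughout and that the SAP departs from the protocol across the board. The documents do not support that reading:

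- SAP 11.1 keeps the protocol's general Grade 3 or higher summary.
- Protocol 9.7 does not set that band for related events, age groups or AESIs as a class. Beyond the general summary it names only non-hematologic toxicities and infections.
- Related Grade 5 events appear in the related-by-severity table, and fatal AESIs in the ungrouped maximum-grade table directly after the collapsed one.
- The age tables do count fatal events, within their all-TEAE and all-related totals. What they lack is a way to tell them apart.
- Deaths are also tabulated by cause, and adverse events are listed by subject.
- No stopping or go/no-go rule in the documents is tied to these rows.

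A further reply is that the table lists are open-ended. That is true of the lists in SAP 11.1.1 and 11.1.2. In SAP 11.2 the similar phrase applies to the AESI categories and terms, not to the tabulations, and the age-group sentence carries no such phrase. In any case, leave to add a table does not prespecify it.

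The reply does not reach three gaps: the missing non-hematologic proportion, the collapsed table with no place for Grade 5, and the absence of any Grade 5 or Grade 3 or higher row by age.

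**Conclusion.** The point holds in a limited form. The clearest gap between the documents is the protocol 9.7 proportion: non-hematologic toxicity has no subject-level row in the SAP, and the severe infection rows stop at Grade 4. The collapsed AESI table excludes any subject whose maximum is Grade 5. By age, fatal events cannot be separated from other events. For related events the gap is smaller: the overview lacks a Grade 5 row, but the information is available elsewhere.

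The size is 1/n per subject missed. Outside the collapsed table this rests on two assumptions: that the fatal event is the subject's only Grade 3 or higher event in that cut, and that such cases occur at all, since every fatal count used here is illustrative. The effect is on how safety is reported, not on any efficacy decision. It is worth correcting because the SAP as written omits a protocol-specified safety proportion.

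**What to change.** In the SAP:

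1. Add the protocol 9.7 rows: subjects with any Grade 3 or higher non-hematologic toxicity, and subjects with any Grade 3 or higher infection. Define which terms count as non-hematologic.
2. In 11.2, change the collapsed bands to maximum grade 1-2 and 3-5.
3. In the age-group, related and AESI severe tables (11.1.1, 11.1.2, 11.2), use Grade 3 or higher and show Grade 5 as a separate row.
4. State whether subjects in severity rows are counted by any event in the band or by maximum grade.

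The cost is SAP wording and minor table-shell work, with no new data. The downside is that some reported severe rates may be slightly less favourable.

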11.3. Deaths

Deaths will be coded according to MedDRA version 21.0 or higher.

Tables summarizing the frequency and percentage of deaths by primary cause of death as reported on the Death eCRF, will be generated by tumor type/disease indication, and in aggregate for each of the following:

- All deaths;
- All death during the Treatment Period (defined as deaths from first pomalidomide dose date to 28 days after the last dose of pomalidomide);
- All death after 28 days after end of treatment.

The incidence of deaths will be subject listings showing MedDRA SOC and PT.

11.4. Second Primary Malignancies

Second primary malignancies are monitored as events of interest and reported as SAEs as an added safety assessment measure. Second primary malignancies are any occurring regardless of relationship to study drug during the conduct of the study including up to 5 years after last subject enrollment date.

Events of SPMs will be tabulated for the following categories:

- All SPMs (invasive and non-invasive);
- All invasive SPMs (hematologic and solid tumor);
- All hematologic SPMs (acute myeloid leukemia, myelodysplastic syndromes, B-cell malignancies, and other hematologic cancers);
- All solid tumor SPMs;
- All non-invasive SPMs (non-melanoma skin cancers).

For each of the above SPM categories, SPMs will be further tabulated using the MedDRA PT. Each subject is counted only once within each SPM category as well as within each PT.

Additionally, the number and percentage of subjects with SPMs who died and those who did not die will be tabulated by SPM category.

It should be noted that these analyses with regard to SPMs are based on the number of subjects with at least one SPM and not the total number of SPMs.

For each SPM category, time to onset will be calculated as time (in months) from the start of the study treatment to the onset of the SPM for each affected subject. For the subjects with more than one new malignancy within an SPM category, the onset of the earliest SPM will be used. Time to onset will be summarized descriptively for each SPM category (n, mean, median, StdDev, Q1, Q3, Min, and Max).

A scatter plot to graphically display the time to onset of hematologic and solid tumor SPMs for each SPM by tumor type/disease indication will be provided.

For each SPM category, the incidence rate per 100 person-years will be calculated as: (the number of subjects with any SPM in the SPM category/total person-years)*100. Total person-years are defined as the total time from the date of first treatment to the first onset date of the specified SPM for subjects with the specified SPM plus the total time from the date of first treatment to the date of the last follow-up or death for subjects without the specified SPM. Incidence rates per 100 person-years and the 95% confidence intervals will be calculated for each tumor type/disease indication and SPM category. Confidence interval at 95% level for the incidence rate per 100 person-years is calculated as follows: $\text{incidence rate} * \exp\{\pm 1.96 * n^{-1/2}\}$.

Listings for “Second Primary Malignancies” and for “Second Primary Malignancies Procedures for Cancers Not Under Study” will be produced by Celgene.

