6.1. Analysis of Primary Efficacy Endpoint

6.1.1. Objective Response and Long-term Stable Disease Rate

The ORSDR is defined as the percentage of subjects that achieve either a CR, PR or SD maintained for ≥ 6 cycles (≥ 3 cycles for the DIPG tumor type/disease indication) as their best response, divided by the total number of subjects available for the analysis within the given population, eg, subjects contained within the Response Population (primary analysis), the ITT Population, and the Safety Population as outlined within Section 5 of this SAP. The ITT Population will not be used should all enrolled subjects have received at least one dose of study drug. Non-responder subjects are considered subjects with a PD as best response, subjects not having a postbaseline assessment or subjects having not evaluable recorded on their postbaseline assessment(s). The corresponding 2-sided, 95% Clopper-Pearson confidence interval (CI) will also be provided.

Calculation of SD duration starts at the time of first dose of pomalidomide and continues until the date of the first observation of PD is recorded or death due to any cause, regardless of whether the subject achieves a CR and/or PR within that period, or until the date of the last disease assessment if no PD or death is recorded; if the difference is ≥ 6 cycles (≥ 3 cycles for the DIPG tumor type/disease indication), ie, the subject has not had a documented PD before Cycle 7, Day 1 (Cycle 4, Day 1 for the DIPG tumor type/disease indication) and has completed 6 cycles of pomalidomide (3 cycles for the DIPG tumor type/disease indication), then the SD will be considered as being maintained for ≥ 6 cycles (≥ 3 cycles for the DIPG tumor type/disease indication).

For identification of PD for this SD duration calculation, PD is classified as a PD as observed during a response assessment (both during the Treatment Period and the Follow-up Period if applicable); the first time this occurrence is observed is selected as the PD date.

Disease assessments recorded on or after start of a new anticancer therapy will not be considered, nor will disease assessments reported after a PD has been observed.

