APPENDIX A1 – REPORTING CONVENTIONS

The summary tables, listings, and any supportive SAS output will include the explanatory “headers” that indicate, at a minimum:

- protocol number;
- database cutoff date, displayed as DDMONYYYY;
- company name (Celgene);
- page number (Page x of x).

The summary tables, listings, and any supportive SAS output will include the explanatory “footers” that indicate, at a minimum:

- program source (ie, SAS program name, including the path, run date);
- data extraction date, displayed as DDMONYYYY;
- data source (ie, list of datasets used for the display);
- run time (ie, when the program was run), displayed as DDMONYYYY:HH:MM.

The purpose of the data extraction date is to link the output to the database, either active or archived, that is write-protected for replication and future reference. The program run date is the output date which will appear on each output page and will indicate the date the output was generated by the analysis program. Individual source listings will display all the relative values supporting corresponding table(s) and figure(s).

In addition, the following reporting conventions will be implemented:

- Data from all study sites will be combined for analysis;
- Confidence intervals (CIs) will be presented as 2-sided 95% CIs unless otherwise specified;
- Summary statistics will consist of the number and percentage of subjects in each category for discrete variables, and the sample size (n), mean, median, standard deviation (StaDev), minimum (Min), and maximum (Max) for continuous variables and displayed as follows:

n	xx
Mean	xx.x
StdDev	xx.xx
Median	xx.x
Q1, Q3	xx.x, xx.x
Min, Max	xx, xx

- For analyses where the sample size, n, is 1, the StaDev will be displayed as ‘NA’;
- All mean and median values will be formatted to 1 more decimal place than the measured value. Standard deviation values will be formatted to 2 more decimal places than the measured value;
- P-values will be rounded to 4 decimal places. P-values that round to 0.0000 will be presented as ‘<0.0001’ and p-values that round to 1.000 will be presented as ‘>0.9999’;

- All percentages will be rounded to 1 decimal place. The number and percentage of responses will be presented in the form xx (xx.x), where the percentage is in the parentheses. In the case the numerator is equal to the denominator, the percentage should be presented as (100) instead of (100.0);

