- If the numerator is '0' then show '0'. If the denominator is '0', then show 'NA' - apply this logic for descriptive stats;
- All listings will be sorted for presentation in order of tumor type/disease indication, study site, subject number, and date of procedure or event. Subjects who are not enrolled will be listed as a non-enrolled group after enrolled subjects;
- In listings, a day reported in relation to treatment start but which is unknown due to an unknown/partially reported date, will be presented with a hyphen;
- In listings, unknown/missing dates will be reported as 'unknown', while the unknown part of a partial date will be presented as 'UN';
- All tables will be presented by tumor type/disease indication;
- In tables where a parameter/category is displayed over several lines, the statistic will be presented on the top line;
- All analysis and summary tables will have the analysis population sample size for each treatment group in the column heading (ie, number of subjects) where applicable;
- Baseline is defined as the latest value collected on or before the date when the first dose of study treatment is administered. If multiple values are present for the same date, the mean of these values will be used as the baseline, except for laboratory data, where the value with the worst Common Terminology Criteria for Adverse Events (CTCAE) grade will be set as baseline. For subjects who were not treated, the baseline value will be defined as the latest value collected on or prior Day 1 of the Cycle 1 visit, if available;
- The day of first dose of study drug pomalidomide will be defined as Day 1. For subjects who are not treated, the Cycle 1 Day 1 visit will be defined as Day 1;
- For tables and figures displaying results by visit, only scheduled visits will be considered beside clinical laboratory evaluations. Unscheduled visits will appear only in listings and could be considered in some derivations;
- The title of the TLG will be centrally justified with the analysis population used directly beneath the title of the TLG, while the TLG number will be in the line directly above the TLG title. The TLG number will be preceded with the text 'Table:', 'Listing:' or 'Figure:', depending on the nature of the output;
- The TLG number will not include alphabetical values;
- The title of the TLG should not include a reference to a footnote;
- The TLG footnotes should follow the following convention for ordering footnotes:
 - Abbreviations

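### The only confidence interval specified for the second primary malignancy rate cannot be computed at zero events, and the SAP gives no other upper bound for that case

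*SAP*

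**What the plan says.** SAP 11.4 defines the rate as "the number of subjects with any SPM in the SPM category/total person-years)*100" and states that "Incidence rates per 100 person-years and the 95% confidence intervals will be calculated for each tumor type/disease indication and SPM category". With four tumor types and five SPM categories (all, invasive, hematologic, solid tumor, non-invasive), that makes 20 cells. The interval is introduced with "Confidence interval at 95% level for the incidence rate per 100 person-years is calculated as follows", followed by the rate multiplied by exp(±1.96 × n^(-1/2)). The symbol n is not defined there, although the same section says its SPM analyses "are based on the number of subjects with at least one SPM and not the total number of SPMs". There is no provision for zero events.

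Two conventions in Appendix A1 bear on the point. One sets the level and sidedness: "Confidence intervals (CIs) will be presented as 2-sided 95% CIs unless otherwise specified". The other governs display when a count is zero: "If the numerator is '0' then show '0'. If the denominator is '0', then show 'NA". For the response endpoints the SAP uses an exact method (SAP 6.1.1: "The corresponding 2-sided, 95% Clopper-Pearson confidence interval (CI) will also be provided"), but it does not extend an exact method to SPMs. Protocol 9.7 plans SPM monitoring and gives no interval for the rate.

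**The concern.** The formula is the large-sample interval on the log rate, with standard error 1/√(events). It needs at least one event, and several events before it is accurate. SPMs in strata of 9 to 20 subjects may well number zero, one or two.

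When no SPM is seen, the observed rate of 0 says little by itself. What a reader needs is how high a rate the data still allow, and that is the figure the formula cannot give. The other four categories are subsets of all SPMs, so a stratum without any SPM loses the interval in all five of its cells. A bare 0 for a stratum with few person-years may then be read as reassurance, or someone must choose a method after seeing the data.

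**Working it through.** **Inputs.** From SAP 11.4: the formula, the 95% level, and the number of subjects with at least one SPM as the numerator of the rate. From SAP 4.4: 9 evaluable subjects per tumor type in stage one and up to 20 in all. The documents state neither an expected SPM rate nor total person-years. The following are therefore assumptions: 0.5, 1 and 2 SPMs per 100 person-years (PY), and 10, 20 and 60 PY per stratum (20 subjects followed for a mean of 0.5, 1 or 3 years). The SAP has no numerical SPM result to reproduce; its multiplier of 1.96 agrees with the normal quantile 1.95996.

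**Step 1: the formula at zero events.**
- If n is the number of subjects with an SPM, n = 0 requires 0^(-1/2), a division by zero. No interval exists.
- If n is the number of subjects (9, 20 or 80), the result is 0 × exp(±1.96/√n), that is 0 to 0. There is still no usable upper limit.

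**Step 2: formula against exact Poisson limits.** With d events, the formula gives d × exp(±1.96/√d). The exact limits are χ²(0.025; 2d)/2 and χ²(0.975; 2d+2)/2. All limits below are in events; divide by PY to obtain a rate.

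| d | SAP formula | Exact | Lower, ratio | Upper, ratio |
|---|---|---|---|---|
| 0 | undefined | 0 to 3.689 | – | – |
| 1 | 0.141 to 7.10 | 0.025 to 5.57 | 5.56 | 1.27 |
| 2 | 0.500 to 8.00 | 0.242 to 7.22 | 2.07 | 1.11 |
| 3 | 0.968 to 9.30 | 0.619 to 8.77 | 1.56 | 1.06 |

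The lowest limit the formula can ever return is 0.141 events. If the true expected count is smaller (0.05 to 0.1, for example, at 0.5 to 1 per 100 PY with 10 PY), every interval it produces excludes the truth.

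**Step 3: the missing upper limit.** At d = 0 the upper limit per 100 PY is 100 × 3.689/PY: 36.9 at 10 PY, 18.4 at 20 PY and 6.1 at 60 PY.

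**Step 4: how often the count is zero.** P(0) = exp(−rate × PY/100).

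| PY | 0.5 per 100 PY | 1 per 100 PY | 2 per 100 PY | Formula returns an interval |
|---|---|---|---|---|
| 10 | 0.951 | 0.905 | 0.819 | 5–18% |
| 20 | 0.905 | 0.819 | 0.670 | 10–33% |
| 60 | 0.741 | 0.549 | 0.301 | 26–70% |

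The last column is 1 − P(0). Each sub-category is at least as likely to be empty as all SPMs together. SAP 11 also calls for safety summaries in aggregate. There P(0) is 0.670, 0.449 and 0.202 with 80 PY, and 0.301, 0.091 and 0.008 with 240 PY. The gap lies mainly in the per-stratum cells.

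**The case against.** Four points can be made for leaving the text alone.

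- **The missing limit would be very wide.** At 10 PY it is 36.9 per 100 PY, which is 18 to 74 times the assumed rates; at 60 PY, 6.1 is still 3 to 12 times them. This is true, and the limit would seldom change a conclusion. But the width is itself the finding: it shows how little a zero count in a small stratum excludes, which a bare 0 does not.
- **Nothing depends on this interval.** SPMs are reported as serious adverse events whatever their cause, the data monitoring committee reviews safety regularly, and counts, time to onset and listings are produced in any case. No threshold or stopping rule uses the interval. This stands and limits the importance of the point.
- **Appendix A1 covers zero counts.** It settles what is printed, so the table can be programmed. It gives no bound.
- **An exact method for one or more events is partly a matter of preference.** The exact interval is itself conservative. Against a mid-P interval at one event (0.050 to 4.93), the formula's lower limit is about 2.8 times too high rather than 5.6, though its upper limit is then 44% too high rather than 27%. A zero-event rule alone would close the main gap. Even so, the formula is poor at one or two events on either benchmark, and one method for all counts is simpler than two.

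**Conclusion.** The concern holds. Under either reading of n, the one interval that SAP 11.4 prescribes gives no upper limit at zero events, and neither document supplies one elsewhere. At one or two events the interval can be computed but is inaccurate: the lower limit is 5.6 and 2.1 times the exact one, and the upper limit is 27% and 11% too high, which errs on the conservative side.

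The failure at zero and the limits by event count follow from the formula alone. How often the problem arises depends on the assumed rates and person-years; within the range shown, a stratum has no SPM with probability between 30% and 95%. The consequence is confined to a descriptive safety output. The plan should be corrected, but neither the primary endpoint nor the stage decisions are at risk.

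**What to change.** Replace the interval sentence in SAP 11.4 with wording such as:

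> Let d be the number of subjects with at least one SPM in the category and T the total person-years. The 95% confidence interval for the rate per 100 person-years is the exact Poisson interval, from 100 × χ²(0.025; 2d)/(2T) to 100 × χ²(0.975; 2d+2)/(2T). When d = 0 the lower limit is 0 and the upper limit is still reported.

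This defines the undefined symbol, uses only quantities SAP 11.4 already derives, and parallels the exact intervals used for the response rates. It costs one sentence and a standard chi-square quantile. The drawback is conservatism at small counts: at expected counts of 0.05, 0.1, 0.2, 0.4 and 1.2 the actual coverage is 99.9%, 99.5%, 98.2%, 99.2% and 99.2%. It falls to about 97.5% just below an expected count of 0.242, where exp(−0.242) × 1.242 = 0.975.
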